### 2.3.3 ASSESSMENT OF POTENTIAL RISKS AND BENEFITS

There is negligible patient risk associated with optimized phlebotomy and clinical decision support. Despite being used safely in multiple clinical trials in critical illness, there are tangible risks of IV iron and EPO therapies. Risks for pharmacologic anemia treatments (IV iron, EPO) will be minimized in multiple ways. First, we will exclude patients at highest risk for potential harm from these therapies, as outlined in the table below:

Exclusion Criteria	Rationale
Iron (IV) or Erythropoiesis-Stimulating Agents (ESA) use in 30 days prior to admission	Already receiving anemia treatment
Pregnancy or breastfeeding	Unclear safety of EPO
Weight <40 kg	Unable to standardize EPO dosing
Uncontrolled sepsis*	Potential infectious risk with IV iron
Allergy to IV iron or erythropoietin	Risk for allergic reaction
Inability to receive VTE pharmacoprophylaxis	Increased thrombosis risk with EPO
Suspected or active thrombosis or myocardial ischemia	Incremental risk with EPO
Uncontrolled hypertension (SBP $\geq$ 190 or DBP $\geq$ 110)	Risk for worsening with EPO
Stroke within 3 months prior	Risk for cerebral ischemia with EPO
Mechanical circulatory support devices (e.g. ECMO, ventricular assist device, Impella)	Risk for device thrombosis with EPO

Hb-hemoglobin. VTE-venous thromboembolism; SBP- systolic blood pressure; DBP-diastolic blood pressure.

\*Uncontrolled sepsis defined by <48 hours of appropriate antimicrobial therapy and/or lack of definitive source control, given theoretical risk for worsening infection with iron supplementation.

Additionally, pharmacological treatments will be targeted to the underlying etiology of anemia to enhance safety. For example, anemia in acute blood loss and iron deficiency is iron-restricted and likely to respond to iron supplementation

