
Regarding EPO, several actions are being taken to mitigate risk: 1) excluding patients with relative contraindications to EPO therapy (e.g. pregnancy, active thrombosis, an inability to receive VTE pharmacoprophylaxis, active myocardial ischemia, poorly controlled hypertension, recent stroke); 2) tailoring pharmacotherapy to anemia etiology, such that EPO is not administered to patients that are likely to mount an appropriate erythropoietic response with iron therapy alone; and 3) providing only a single dose of EPO therapy for those receiving this therapy. Of note, the optimal dosing of EPO is unknown in the critically ill, though clinical trials in surgical patients have shown that a single dose of EPO results in sustained hemoglobin improvement. All adverse events will be closely evaluated by study personnel as outlined in the data safety monitoring plan. Similar to iron, EPO will be administered by critical care nurses in accordance with institutional medical administration protocols. Iron will be co-administered immediately prior to EPO to ensure adequate iron stores for EPO-induced augmentation of bone marrow erythropoiesis. Patients will be continuously monitored at the time of administration for immediate adverse effects (e.g. cutaneous reactions, hypertension, dizziness, nausea). Those without immediate reaction will be observed clinically for 1 hour post-infusion for the

development of delayed reactions with blood pressure measurements at least every 15 minutes, continuous pulse oximetry, and telemetry. Those experiencing infusion reactions will be observed for longer times as dictated by the severity of the reaction.

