## 5.2 EXCLUSION CRITERIA

An individual who meets any of the following criteria will be excluded from participation in this study:

1. IV iron or any ESA use (i.e. darbepoetin, Aranesp, erythropoietin, Epojen, Procrit, Retacrit) within 30 days of enrollment. Oral iron is permitted (e.g. oral iron supplements, multivitamin with iron)
2. Severe anemia prior to hospitalization (i.e. hemoglobin consistently  $< 9$  g/dL in the 90 days prior to admission). If hemoglobin is not available or if hemoglobin is  $\geq 9$  g/dL at any time within 90 days prior to enrollment, then this criterion is not met, and the patient may be enrolled
3. Known allergic reactions to IV iron or any EPO agent
4. Inability to complete outcome assessments (i.e. not expected to survive hospitalization, unable to make follow-up appointments, non-ambulatory status preceding hospitalization, dementia or other severe cognitive impairment, visual impairment i.e. blind or legally blind, non-English speaking)
5. Pregnancy or breastfeeding at time of enrollment given unclear safety of EPO
6. Inability to receive pharmacologic venous thromboembolic prophylaxis except in patients with acute blood loss anemia (i.e. recent surgery or gastrointestinal bleeding, extracranial bleeding)
7. Active or suspected thrombosis (i.e. DVT, pulmonary embolism, acute arterial thrombus) within 3 months except in patients with acute blood loss anemia (i.e. recent surgery, gastrointestinal bleeding, extracranial bleeding)
8. Uncontrolled sepsis (i.e. lack of definitive source control and/or  $< 48$  hours of appropriate antimicrobial therapy)
9. Having received  $\geq 10$  units of allogeneic RBCs in the 48 hours before enrollment
10. Acute coronary syndrome (STEMI or NSTEMI) or ischemic stroke within 3 months except in patients with acute blood loss anemia (i.e. recent surgery, gastrointestinal bleeding, extracranial bleeding)
11. Weight less than 40 kg
12. Concerns with study enrollment expressed by the clinical team

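### Section 2.3.3 promises safety exclusions for EPO that the working list in 5.2 omits or covers only in part

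*Combined protocol and SAP*

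**What the plan says.** Section 2.3.3 introduces its table with a commitment: "First, we will exclude patients at highest risk for potential harm from these therapies, as outlined in the table below". The table pairs each of 10 conditions with a rationale. One row is "Suspected or active thrombosis or myocardial ischemia", justified by added risk with EPO. Another is uncontrolled hypertension (SBP ≥190 or DBP ≥110), which EPO may worsen. A third is mechanical circulatory support, because of device thrombosis. The stroke row reads "Stroke within 3 months prior", with the rationale "Risk for cerebral ischemia with EPO". No row carries an exception for blood loss. The EPO paragraph later in 2.3.3 repeats the point, listing "active myocardial ischemia, poorly controlled hypertension, recent stroke" among the relative contraindications handled by exclusion.

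Section 5.2 has 12 criteria. Those bearing on EPO safety are:

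- Criterion 6: "Inability to receive pharmacologic venous thromboembolic prophylaxis except in patients with acute blood loss anemia".
- Criterion 7: "Active or suspected thrombosis (i.e. DVT, pulmonary embolism, acute arterial thrombus) within 3 months except in patients with acute blood loss anemia".
- Criterion 10: "Acute coronary syndrome (STEMI or NSTEMI) or ischemic stroke within 3 months except in patients with acute blood loss anemia".
- Criterion 12: a concern raised by the clinical team, with no defined trigger.

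No criterion mentions blood pressure or a support device. Section 5.5 has coordinators screen health records against the inclusion and exclusion criteria. Section 6.1.1 then gives a single 40,000-unit dose of EPO to intervention-arm patients whose anemia is not iron-responsive.

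**The concern.** The protocol holds two exclusion lists. The one that justifies the risk is wider than the one that decides enrollment. Staff who follow 5.2 exactly could enroll, and dose with EPO, a patient whom 2.3.3 tells the IRB and other readers is kept out because of EPO.

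The conditions are not incidental. Section 2.3.1 cites the boxed warning for myocardial infarction, stroke and thrombosis, and names uncontrolled hypertension among the rare major reactions. Section 8.3.1 monitors for hypertensive urgency in the hour after dosing. What is at stake is participant safety and the accuracy of the stated risk assessment, not the efficacy inference.

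**Working it through.** No formula applies, because the documents give no frequency for any of these conditions. The check sets each row of the 2.3.3 table against 5.2.

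| 2.3.3 row | 5.2 criterion | Result |
|---|---|---|
| Pregnancy or breastfeeding | 5 | match |
| Weight <40 kg | 11 | match |
| Uncontrolled sepsis | 8 | match |
| Allergy to iron or EPO | 3 | match |
| No VTE pharmacoprophylaxis possible | 6 | match, with added acute-blood-loss exception |
| IV iron or ESA in prior 30 days | 1 | in part: counted back from admission in 2.3.3, from enrollment in 5.2 |
| Thrombosis or myocardial ischemia | 7 and 10 | in part: ischemia only as STEMI/NSTEMI or arterial thrombus; exception added |
| Stroke within 3 months | 10 | in part: ischemic only; exception added |
| Uncontrolled hypertension | none | no criterion |
| Mechanical circulatory support | none | no criterion |

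Count: 4 + 1 + 3 + 2 = 10.

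**Iron/ESA window.** Take a dose given 28 days before admission to a patient enrolled 5 days after admission. That dose is 28 + 5 = 33 days before enrollment. The patient is excluded under 2.3.3 (28 is within 30) but not under 5.2 (33 is not).

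**Route to EPO.** Consider a patient with SBP above 190, or on a ventricular assist device, or with ischemia still under work-up. Suppose there is no thrombus, no infarction diagnosis and no other exclusion, and the anemia is neither from blood loss nor from iron deficiency.

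1. None of criteria 1 to 11 applies. Only the discretionary criterion 12 could stop enrollment.
2. The PI or a co-investigator adjudicates etiology and treatment before randomization (4.1, 6.1.1), from iron studies and clinical history. No check for ischemia, blood pressure or devices is named. The schedule of activities records baseline blood pressure without a stopping threshold, and lists no ECG or troponin.
3. If randomized to the intervention, the patient is assigned EPO under 6.1.1.
4. Withdrawal under 7.2 is possible. However, the drug is a single dose given straight after randomization, so withdrawal after that point cannot prevent exposure.

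**Blood-loss exception.** Criteria 6, 7 and 10 are waived for acute blood loss anemia, with no volume stated. Section 4.1 puts acute blood loss in the iron-alone group, also without a volume. In 6.1.1 the iron-alone group requires a loss of at least 500 ml (or iron deficiency), while the EPO group is defined as anemia not due to acute blood loss, again without a volume. A patient with a smaller loss and no iron deficiency is therefore assigned to iron alone by 4.1 but clearly placed by neither definition in 6.1.1.

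**The case against.** The strongest case against is that criterion 10 is simply the operational form of the undefined term in 2.3.3. It names the acute coronary diagnoses and adds a 3-month look-back that the table row lacks, and criterion 7 adds suspected arterial thrombus. The EPO paragraph calls these relative contraindications, which can reasonably be left to judgment, and two judgment steps precede randomization. The screening form and the institutional drug-administration guidelines are not in the documents and may contain the missing checks. Finally, excluding iron-only patients for a risk specific to EPO would be excessive.

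Part of this stands. For ischemia the gap is narrow: the condition must be neither infarction nor thrombotic, must go unflagged by clinicians, must occur with anemia that is not iron-responsive, and the patient must be randomized to the intervention. That is why the two rows with no criterion are the stronger part of the point. The argument about operational form does not reach them, because 5.2 has nothing that could be an operational form of either.

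Discretion is also not what 2.3.3 describes: it says these patients will be excluded. An unseen form might close the gap in practice, but the protocol would still contain two conflicting lists. The concern about iron-only patients is fair and is met by limiting the new criteria to the EPO stratum if the sponsor prefers.

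**Conclusion.** The inconsistency is real and worth correcting. Two of the 10 table rows have no criterion in 5.2, three are matched in part, and one gains an exception. The number of patients exposed as a result cannot be estimated from the documents and is likely small. Most of the mitigation stands: STEMI/NSTEMI, ischemic stroke and thrombosis are excluded outside acute blood loss, and EPO is a single dose restricted by etiology. Sample size, power and the primary analysis are untouched.

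Two stronger readings are tempting but not supported.

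- A reader might infer that the acute-blood-loss exception sends patients with recent thrombosis or infarction to EPO. It does not by itself: 4.1 and the EPO-group definition in 6.1.1 both keep acute blood loss out of the EPO group without a volume limit. Only the 500 ml threshold in the iron-alone definition disagrees. That is a wording conflict to settle, not a shown route to EPO.
- A reader might take the stroke row as a further gap. Its rationale refers to cerebral ischemia and 8.3.1 monitors non-hemorrhagic stroke, so ischemic stroke may be all that was meant. It is an ambiguity.

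The conclusion assumes that 5.2 governs enrollment, as 5.5 indicates, and that no unseen document adds the missing checks.

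**What to change.** Add three criteria to 5.2: uncontrolled hypertension (SBP ≥190 or DBP ≥110), mechanical circulatory support, and suspected or active myocardial ischemia. Keep them separate from criterion 10, because placing ischemia there would subject it to the blood-loss exception, which the 2.3.3 row does not have. State what counts as suspected ischemia in terms a coordinator can read from the record. The criteria should apply at least to patients adjudicated to the EPO stratum. Etiology is settled before randomization, so this restriction can be applied in both arms alike.

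If 5.2 was narrowed on purpose, correct the 2.3.3 table and the EPO paragraph instead, and restate the risk assessment.

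In the same edit:

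- Use one stroke definition in 2.3.3 and 5.2.
- Use one reference date for the 30-day iron/ESA window.
- Make 4.1 and both group definitions in 6.1.1 agree on whether acute blood loss under 500 ml belongs to the iron-alone group, so that nobody enrolled under the exception in criteria 6, 7 or 10 receives EPO.
- Show that exception in the 2.3.3 table.

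The cost is one IRB-approved amendment, matching changes to whatever screening form is in use, and some additional screen failures, whose number the documents do not allow one to estimate.

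### Two EPO-risk exclusions promised in Section 2.3.3, uncontrolled hypertension and mechanical circulatory support, are missing from the eligibility criteria and the dosing rules

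*Combined protocol and SAP*

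**What the plan says.** Section 2.3.3 introduces its exclusion table with a commitment: "First, we will exclude patients at highest risk for potential harm from these therapies, as outlined in the table below". The table has ten rows. The uncontrolled hypertension row (SBP at or above 190 or DBP at or above 110) gives as its reason "Risk for worsening with EPO". The last row, "Mechanical circulatory support devices (e.g. ECMO, ventricular assist device, Impella", gives device thrombosis with EPO as its reason.

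Further on, 2.3.3 lists three ways of containing EPO risk. The first is to exclude patients with relative contraindications, among them "active myocardial ischemia, poorly controlled hypertension, recent stroke"; devices are not named there. The second is that "EPO is not administered to patients that are likely to mount an appropriate erythropoietic response with iron therapy alone". The third is "providing only a single dose of EPO therapy for those receiving this therapy".

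Section 5.2 opens with "An individual who meets any of the following criteria will be excluded from participation in this study" and lists twelve items. None mentions blood pressure or a circulatory device. The only general item is number 12: "Concerns with study enrollment expressed by the clinical team".

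Section 6.1.1 assigns 40,000 units of EPO to every intervention patient whose anemia is not iron-responsive. Section 6.1.2 fixes the dose for all, and Section 4.1 states that everyone in the intervention arm gets iron, EPO or both.

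**The concern.** Two sections of one protocol disagree on who may be enrolled, and the patients in dispute are those the protocol itself places at highest risk. Under Section 5.5, coordinators screen records from any adult ICU against the inclusion and exclusion criteria, and 5.1 and 5.2 are the sections that carry that name. A criterion found only in a background table can be missed.

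Section 2.3.1 counts uncontrolled hypertension among the rare major reactions to EPO and cites a boxed warning that covers thrombotic events. If the two criteria are not applied, the risk argument in 2.3.3 describes protection that the trial does not give. It is also unclear whether enrolling such a patient would be a protocol deviation: by 2.3.3 it would, by 5.2 it would not.

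**Working it through.** No statistical figure is involved. The check sets each row of the 2.3.3 table against the numbered items in 5.2.

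| Row in 2.3.3 table | Item in 5.2 | Reason tied to EPO? |
|---|---|---|
| 1. Recent IV iron or ESA | 1 | no |
| 2. Pregnancy or breastfeeding | 5 | yes |
| 3. Weight under 40 kg | 11 | yes |
| 4. Uncontrolled sepsis | 8 | no |
| 5. Allergy to iron or EPO | 3 | no |
| 6. No VTE pharmacoprophylaxis | 6 (relaxed for acute blood loss) | yes |
| 7. Thrombosis or myocardial ischemia | 7 and 10 (relaxed for acute blood loss) | yes |
| 8. Uncontrolled hypertension | none | yes |
| 9. Stroke within 3 months | 10 (ischemic only; relaxed for acute blood loss) | yes |
| 10. Mechanical circulatory support | none | yes |

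Counts:
- Rows with at least a partial counterpart: 10 − 2 = 8.
- Rows with an EPO-related reason: 7 (rows 2, 3, 6, 7, 8, 9, 10). Carried into 5.2 at least in part: 5. Missing: 2.
- Items in 5.2 that name blood pressure or a circulatory device: 0 of 12. Items in 5.1 that do: 0 of 7.

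Other places where a check could sit:
- **1.3:** blood pressure is recorded at enrollment, but no eligibility or dosing rule uses it.
- **6.1.1 and 6.1.2:** no blood pressure or device condition for withholding EPO. EPO is to follow institutional guidelines whose content is not given.
- **7.2:** withdrawal for meeting an exclusion criterion is optional and comes after enrollment.
- **8.2 and 8.3.1:** blood pressure is monitored during administration, and a hypertensive event is recorded in the hour after it. Neither decides who is dosed.

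The two gaps differ from the relaxations in items 6, 7 and 10. Those apply only to acute blood loss, and 6.1.1 gives such patients iron alone when the loss is at least 500 ml, so they largely keep EPO away from the patients concerned. Rows 8 and 10 are missing for everyone, including the group assigned EPO.

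Ceiling on exposure: 1:1 allocation of 100 patients puts about 100 / 2 = 50 in the intervention arm, and only those with non-iron-responsive anemia receive EPO. The documents give neither that share nor the frequency of the two conditions.

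**The case against.** The strongest reply is that the protocol should be read as a whole. The 2.3.3 table is headed as exclusion criteria and is phrased as a commitment, and 5.5 does not confine screening to 5.2. On that reading these patients are excluded and 5.2 is merely incomplete. That is fair as interpretation, but it concedes that the list needs completing.

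There are also real safeguards:
- The principal investigator or a co-investigator adjudicates etiology and treatment before randomization (4.1, 6.1.1).
- Patients are monitored during EPO administration and for an hour afterwards, with blood pressure at least every 15 minutes (2.3.3).
- The clinical team can object under item 12.
- Items 4, 6, 7 and 10 will catch some of these patients for other reasons.

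None is a stated blood pressure or device check before dosing. The adjudication concerns etiology, monitoring detects harm once the drug is being given, item 12 depends on someone objecting, and item 7 concerns an existing or suspected clot, not a device at risk of one.

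The two rows may also have been dropped on purpose. Section 5.2 departs from the table in considered ways, such as the blood-loss exceptions and the restriction to ischemic stroke, which would fit a later revision. The documents do not settle this. If it is so, 2.3.3 is the section in error.

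A reader might infer two stronger things that the documents do not support. One is that the first EPO mitigation is lost for an affected patient. That mitigation is a set of exclusions, and those for pregnancy, VTE prophylaxis, thrombosis, acute coronary syndrome and ischemic stroke still apply as 5.2 words them. The other is that the gap undermines the hypertensive adverse event, whose absolute threshold is SBP 200. With the limit of 190 restored, a patient at 189 could still enroll and reach the threshold with a rise of 200 − 189 = 11 mmHg. That event is also defined by study drug administration, which the standard-care arm does not have, so the gap cannot distort a between-arm comparison of it.

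**Conclusion.** The inconsistency is real. Two of ten exclusions that 2.3.3 relies on, both among the seven with an EPO reason, have no counterpart in 5.1, 5.2 or 6.1. The text therefore permits EPO in a patient whom 2.3.3 says will not be in the trial. The EPO safety case is weakened, not void: etiology targeting, single dosing, most of the contraindication exclusions and the monitoring around dosing remain. The primary estimand, power and analysis are not affected.

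Confidence is high for the mismatch in the text and limited for patient exposure. Exposure assumes screening on 5.2 as written, no blood pressure or device hold in the institutional EPO guidelines, and an eligibility form that does not already carry the two items. Neither the guidelines nor the form is in the documents. It would go too far to conclude that such patients will be dosed, or that the omission was an oversight. The contradiction still warrants correction, because it concerns eligibility for a drug with a boxed warning and is cheap to remove.

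**What to change.** Add both criteria to 5.2 and to the eligibility form, worded as in the 2.3.3 table. Apply them at least to patients whose adjudicated etiology would lead to EPO. Because etiology is settled before randomization, the rule then works identically in both arms. For hypertension, use the blood pressure already recorded at enrollment under the schedule of activities; device use is evident at screening, so no new data are needed.

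If the sponsor confirms that the criteria were dropped deliberately, take both rows out of the 2.3.3 table, take hypertension out of the EPO mitigation text (devices are not mentioned there), and justify the EPO risk without them.

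The cost of adding the criteria is two lines in a short amendment, one form change and slightly fewer eligible patients.

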### 3 OBJECTIVES AND ENDPOINTS

OBJECTIVES	ENDPOINTS	JUSTIFICATION FOR ENDPOINTS
Primary		
To assess the efficacy of the intervention on mean difference in hemoglobin concentrations at 1 month post-hospitalization	Hemoglobin concentrations [Time frame: 1 month post-hospitalization]	Hemoglobin concentrations are widely available to infer changes in RBC mass from anemia management interventions
Secondary		
To assess the impact of the intervention on hemoglobin concentrations through 3-months post hospitalization	Hemoglobin concentrations [Time frame: through 3 months post-hospitalization]	Hemoglobin concentrations are widely available to infer changes in RBC mass from anemia management interventions
To assess the impact of the intervention on phlebotomy draws and volumes throughout hospitalization	Phlebotomy draws and volumes [Time frame: through hospitalization]	Phlebotomy draws and volumes are utilized to assess the efficacy of optimized phlebotomy and clinical decision support
To assess the impact of the intervention on quality of life after critical illness	EQ-5D [Time frame: hospital discharge, 1 month, and 3 months post-hospitalization]	Quality of life patient-reported outcome recommended as part of Core Outcome Measurement Set (COMS) for ICU survivors
To assess the impact of the intervention on fatigue after critical illness	PROMIS-Fatigue [Time frame: hospital discharge, 1 month, and 3 months post-hospitalization]	Anemia-related fatigue patient-reported outcome
To assess the impact of the intervention on physical function after critical illness	6-minute walk distance, activity-monitoring daily step count and energy expenditure (optional), activities of daily living survey [Time	Recommended as part of Core Outcome Measurement Set (COMS) for ICU survivors

OBJECTIVES	ENDPOINTS	JUSTIFICATION FOR ENDPOINTS
	frame: 1 and 3-months post-hospitalization]	
To assess the impact of the intervention on cognitive function after critical illness	MoCA-BLIND [Time frame: 1 and 3-months post-hospitalization]	Recommended as part of Core Outcome Measurement Set (COMS) for ICU survivors
To assess the impact of the intervention on mental health after critical illness	HADS, IES-R [Time frame: 1 and 3-months post-hospitalization]	Recommended as part of Core Outcome Measurement Set (COMS) for ICU survivors
To assess the impact of the intervention on RBC transfusions	Allogeneic RBC transfusions (units) [Time frame: hospitalization, through 3-months post-hospitalization]	Anemia management may directly result in reductions in RBC transfusions
To assess the impact of the intervention on unplanned hospital readmissions through 12-months post-hospitalization.	Unplanned hospital readmissions [Time frame: 12 months]	Previous data suggests that anemia treatment with iron therapies may reduce hospital readmissions
To assess the impact of the intervention on mortality through 12-months post-hospitalization	All-cause mortality [Time frame: 12 months]	Previous data suggests that IRON and EPO may reduce mortality during and after critical illness

